4.7.3 Vital signs, ECG and physical examination

All assessments will be performed at time points indicated in the flow chart (Table 1).

Formatted: Bullets and Numbering

4.7.3.1 Methods of assessment

Vital signs

Vital signs comprise the assessment of systolic and diastolic blood pressure, pulse, respiratory rate and body temperature. Assessments of vital signs resulting in clinically significant abnormal values will be repeated, in order to exclude an erroneous assessment. Controls will also be necessary if implausible measurements occur, e.g., significant deviations from previous assessments. Individual results will be classified as 'normal', 'abnormal with no clinical significance' and 'abnormal with clinical significance'. Abnormal values 'with no clinical significance' may be considered clinically significant if they are accompanied by clinical symptoms such as dizziness, tiredness, nausea or vomiting etc.

All measurements of vital signs will be done according to the applicable SOP.

Twelve-lead ECG

Twelve-lead ECGs will be recorded in accordance with local procedure.

A resting ECG will be recorded at Visit 1 for confirmation of study eligibility and at Visit 5 for follow-up safety assessment. Further ECG recordings will be performed according to the study plan (Table 1). ECGs will be recorded in the supine position after the patient has rested in this position for at least 10 minutes. Only overall evaluation will be captured in Any abnormalities (including QTc values) should be reviewed by a cardiologist or an appropriately qualified person.

The original ECGs and variables must be signed and dated and stored in the patient's medical record as source data.

Telemetry

Ambulatory cardiac monitoring will be performed using CardioMem CM3000 recorders (Getemed, Germany) from 24 hours pre-dose to 24 hours post first dose at Visit 2. The Investigator or delegate will review and evaluate the recordings before dosing, and before discharge. A print-out will be signed and dated by the Investigator and filed with the CRF.

Physical examination

A full physical examination will be performed to ensure suitability according to the inclusion and exclusion criteria at the Screening visit. The physical examination comprises a routine medical examination including gross neurological assessments. Measurement of body weight and height will be done as well.

The physical examination will be repeated as the follow-up visit and any new findings should be recorded as adverse events.

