AZD9668, a pyridone of molecular weight of 545.5 g/mol, is a potent, oral, selective, reversible inhibitor of human NE. It is being developed as a possible therapeutic agent both for symptomatic treatment as well as disease modification in COPD. Orally administered AZD9668 produced a dose-dependent inhibition of human NE-induced lung haemorrhage in the mouse. Mice exposed to cigarette smoke and treated with AZD9668 showed a significant reduction in total number of cells and neutrophils and IL1- β , compared to vehicle treated smoke exposed mice, indicating the possibility of inhibiting endogenously released NE with this drug.

AZD9668 was well tolerated in rat and dog toxicity studies. In a dog 28-day toxicity study minor hematological abnormalities were noted at high doses. There was no bone-marrow pathology. Electrophysiological studies showed a hERG IC50 of 69 μ M, and *in vivo* a slight QT-prolongation (9%) at a high dose in a dog telemetry study. Mutagenicity tests indicated that AZD9668 does not pose a significant genotoxicity risk.

A first administration to man, Phase I, randomised, double blind, placebo-controlled, 2-part study (D0520C00001) to assess the safety and tolerability and pharmacokinetics of single and multiple oral doses of AZD9668 in healthy volunteers has been completed.

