4.7.3.2 Derivation or calculation of outcome variables

All individual values and changes to baseline will be listed and summarized descriptively.

Abnormal findings for vital signs and ECGs should only be reported as AEs if they are accompanied by clinical symptoms, constitute SAEs or lead to discontinuation of treatment with the investigational product.

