6.4.4 Safety analysis

Examination of the following safety variables will address the primary objective to investigate the tolerability of 14 days' treatment with AZD9668. No formal hypotheses will be associated with these variables, although informal comparisons will be made between treatment groups to determine whether there appears to be any treatment-related effects: adverse events, vital signs, 12-lead ECG (overall evaluation), lung function, sputum bacteriology, safety lab data (clinical chemistry, haematology, urinalysis), physical examination and concomitant medication.

Adverse events will be analysed by means of descriptive statistics and qualitative analysis. AEs will be listed for each patient and summarised by System Organ Class and preferred term assigned to event by using MedDRA 10.0.

Concomitant medications will be classified according to the AZDD Drug Dictionary, the ATC system and the CPMP route of administration dictionary. All concomitant medications reported at entry and recorded during the study will be summarised and listed.

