- Evidence of haemolysis as evidenced by the following:
 - Reticulocyte count of over 5%, and

At least two of the following:

- a drop in haemoglobin below 10.5 g/dl
- decrease of 25% in haptoglobin. (The value post-dose to be compared with the average of two pre-dose values. The value should also be 15% below LLN).
- increase of 25% in unconjugated bilirubin or lactate dehydrogenase (LDH).
 (The value post-dose to be compared with the average of two pre-dose values. The value should also be 15% above ULN)
- A platelet count of below $80 \ge 10^9$ /L confirmed by a repeat test (in the absence of obvious platelet clumping in a peripheral blood film).
- A QTcF >500 ms on active treatment (QT interval corrected for heart rate by Fridericia method) or a QTcF prolongation >60 ms on average compared to baseline, confirmed by a repeat ECG in 30 minutes.

Section of protocol affected:

3.3.5, Discontinuation of patients from treatment or assessment3.3.5.1, Criteria for discontinuation, Stopping criteria for the whole study, page 30

Previous text:

Stopping criteria for the whole study

- Two or more patients on active treatment are discontinued because of either an ALT/AST level ≥3 x ULN or any pattern of LFT abnormalities giving cause for concern
- Two or more patients on active treatment are discontinued because of evidence of haemolysis
- Two or more patients on active treatment are discontinued because of a platelet count of below $80 \times 10^9/L$

Revised text:

Stopping criteria for the whole study

- Two or more patients on active treatment are discontinued because of either an ALT/AST level ≥3 x ULN or any pattern of LFT abnormalities giving cause for concern
- Two or more patients on active treatment are discontinued because of evidence of haemolysis
- Two or more patients on active treatment are discontinued because of a platelet count of below $80 \ge 10^9/L$
- A QTcF >500 ms on active treatment (QT interval corrected for heart rate by Fridericia method) or a QTcF prolongation >60 ms on average compared to baseline, confirmed by a repeat ECG in 30 minutes in 2 or more subjects on active treatment

Section of protocol affected:

Section 10, References, page 58

Added reference:

GOLD 2007

Global Initiative for Chronic Obstructive Lung Disease. Global Strategy for the Diagnosis, Management, and Prevention of Chronic Obstructive Pulmonary Disease. Updated 2007. http://www.goldcopd.org

Reason for Amendment:

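### Only an overall ECG evaluation is captured and analysed, which conflicts with the promised values and changes from baseline and leaves the QTcF data behind Amendment 01 outside the study dataset

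*Protocol*

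**What the plan says.** ECG is part of the first primary objective, tolerability (protocol Section 2.1).

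- **Capture.** Section 4.7.3.1 states "Only overall evaluation will be captured in" the study system. The numeric readings go elsewhere: "The original ECGs and variables must be signed and dated and stored in the patient's medical record as source data". Individual review is required: "Any abnormalities (including QTc values) should be reviewed by a cardiologist or an appropriately qualified person".
- **Derivation.** Section 4.7.3.2, under the heading covering vital signs, ECG and physical examination, says: "All individual values and changes to baseline will be listed and summarized descriptively". It then limits AE reporting of ECG findings to those that are symptomatic, serious or lead to discontinuation.
- **Analysis.** Section 6.4.4 lists the safety variables and gives the ECG entry as "12-lead ECG (overall evaluation" (closing bracket cut here).
- **Criteria.** Amendment 01 adds to Section 3.3.5.1 a patient discontinuation criterion: QTcF above 500 ms, "or a QTcF prolongation >60 ms on average compared to baseline, confirmed by a repeat ECG in 30 minutes". The same limits in two or more subjects on active treatment become a stopping criterion for the whole study.
- **Why QT is of interest.** Section 1.1 reports "a slight QT-prolongation (9%) at a high dose in a dog telemetry study". Section 3.2.1 explains that morning doses are given fasted on Days 1, 7 and 14 so that ECGs can be taken when Cmax is at its highest.

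**The concern.** An overall evaluation is a category. It has no numeric value to list and no numeric change from baseline, so Sections 4.7.3.1 and 6.4.4 do not fit Section 4.7.3.2. The amendment widens the gap. Both new criteria need a numeric QT, a heart rate for the Fridericia correction and a baseline. Yet the amendment, as shown, changes neither the capture rule nor the analysis rule, and it does not say which pre-dose ECG is the baseline.

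What is at stake is the report on a primary tolerability variable. The protocol times ECGs to high exposure and excludes patients on QTc because of a preclinical finding, but the dataset would hold nothing from which to estimate a mean QTcF change by treatment. The individual criteria are no substitute, because they are built to catch extremes.

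**Working it through.** **1. The texts side by side**

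| Place | What it requires |
|---|---|
| 4.7.3.1 | Overall evaluation captured; numeric variables kept in the medical record |
| 6.4.4 | Overall evaluation analysed |
| 4.7.3.2 | Individual values and changes from baseline listed and summarised |
| Amendment 01, to 3.3.5.1 | QTcF level and change from baseline, per patient and across patients |

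The blacked-out word in Section 4.7.3.1 hides the name of a system, not the rule, because Section 6.4.4 repeats the restriction independently.

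**2. Would the QTcF criteria reveal a moderate mean shift?**

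The protocol gives no figure for this, so there is none to reproduce.

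- From the documents: 18 patients randomised 2:1, so 18 × 2/3 = 12 active and 18 × 1/3 = 6 placebo; limit of +60 ms.
- Assumed: normally distributed QTcF change, SD 10, 15 or 20 ms, true mean rise 10 or 20 ms, one reading per patient.

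Per-patient chance: p = 1 − Φ((60 − mean)/SD). Chance that at least one of 12 exceeds the limit: 1 − (1 − p)^12.

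For a mean rise of 20 ms:

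- SD 10: z = 40/10 = 4.00, p = 0.000032, at least one of 12 = 0.04%
- SD 15: z = 40/15 = 2.67, p = 0.00383, at least one of 12 = 4.5%
- SD 20: z = 40/20 = 2.00, p = 0.02275, at least one of 12 = 24.1%

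For a mean rise of 10 ms, the corresponding chances are below 0.1%, 0.5% and 7.2%. The chance of two or more, which the study-level criterion needs, is at most 2.9% across this range. Several on-treatment ECGs per patient would raise these figures; the required confirmation by a repeat ECG would lower them.

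**3. What captured values would give**

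Standard error of the active–placebo difference in mean change: SE = SD × √(1/12 + 1/6) = SD × 0.5. With 16 degrees of freedom, t = 2.12.

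- SD 10: SE 5.0 ms, 95% CI half-width 10.6 ms
- SD 15: SE 7.5 ms, half-width 15.9 ms
- SD 20: SE 10.0 ms, half-width 21.2 ms

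A 20 ms difference would stand clear of zero for SD 10 or 15, but not quite for SD 20. A 10 ms difference would not in any of the three.

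**4. Volume of data**

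Scheduled ECGs per patient (Table 1, note b): screening, Day −1, Day 1, Day 2, Day 3, Day 7, Day 14 pre-dose, Day 14 at 1 h, follow-up = 9. Then 9 × 18 = 162 records.

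**The case against.** **The data exist.** The ECG variables are kept as source data and abnormal QTc values must be reviewed. The investigator can apply the amendment's limits from source without any database field, and a discontinuation under them is reportable as an AE. This stands. A reader might infer that the trial would hold no data able to show a QT effect, or that the criteria cannot be operated; the documents support neither. What is missing is capture in the study dataset, and hence a summary in the report.

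**The derivation sentence is generic.** It could be read as applying to whatever is captured, with a shift table of categories serving for ECG, and output detail is left to the SAP. That softens the contradiction in wording. It does not restore the lost information: an SAP can summarise only what was captured, unless someone returns to source later.

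**The dog finding should not be carried into patients.** It is tempting to argue that 9% on an assumed 400 ms baseline (400 × 1.09 = 436 ms) would be rated normal throughout. The documents do not support this.

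- The protocol calls the effect slight and at a high dose, and reports no QT prolongation in healthy volunteers (Sections 1.1 and 3.2.2).
- The 450 ms figure is an entry limit, 470 ms for females after Amendment 01; nothing makes it the cut-off for the overall evaluation.
- Even on that limit, any baseline above 450/1.09 ≈ 413 ms would pass 450 ms.
- With a 36 ms rise and SD 10 to 15 ms, the chance that at least one of 12 exceeds +60 ms is about 9% to 49%. A shift of that size is not reliably hidden.

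**The phrase *on active treatment*.** A reader might infer that blinded staff cannot apply the patient-level criterion. The phrase may simply mean during dosing, and Section 3.6.2 already allows unblinding when two or more patients meet discontinuation criteria. But the study-level criterion uses the same words for the active arm, so they are ambiguous and need clarifying.

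**Conclusion.** The conflict holds. Sections 4.7.3.1 and 6.4.4 confine ECG data to an overall evaluation, Section 4.7.3.2 promises more, and Amendment 01 adds numeric QTcF criteria without bringing the values into the dataset. The consequence is limited but real. Large individual prolongations can be caught through source review and the criteria; a moderate mean QTcF shift would be absent from the dataset and the report. Under the assumed 20 ms rise with SD 10 to 20 ms, the +60 ms limit would be crossed by any active patient with a chance of only about 0.04% to 24%.

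The mean rise, the SDs, normality and the single reading per patient are assumptions, not figures from the protocol. Nothing here suggests that a QT effect is expected at the study dose, and the small sample would give an estimate rather than a test. That suits a study that tests no hypotheses (Section 6.2).

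**What to change.** Reconcile Sections 4.7.3.1, 4.7.3.2 and 6.4.4 with the QTcF criteria added by Amendment 01:

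- Capture heart rate and QT, and the other intervals already measured, from every scheduled ECG and from any confirmatory repeat; derive QTcF.
- Define the pre-dose baseline. Screening and Day −1 both precede dosing, and the Day 1 ECG is taken after the dose.
- In Section 6.4.4, list and summarise QTcF and its change from baseline by treatment and time point, including the 1 h post-dose ECGs on Days 1 and 14, with counts above the amendment's own thresholds. Keep the overall evaluation alongside.
- Clarify *on active treatment* in the patient-level criterion and reconcile it with Section 3.6. The clinical limits themselves are not at issue.

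Cost: about 160 transcribed records (162 scheduled, plus any repeats) and one descriptive table, with no new patient procedure. Fixing this before unblinding also avoids selective retrieval from source afterwards. The report should give the estimate with its interval and say that the study was not designed to exclude a QT effect.

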Patients will attend the CPU in fasted state with their BronkoTest[©] diary card on the morning of Day -1 and stay until Day 3. Eligibility will be re-confirmed and safety assessments performed (vital signs, ECG, lung function, haematology, clinical chemistry and urinalysis, urine drug screen including alcohol). Twenty-four hour ambulatory cardiac monitoring (telemetry) will be started on Day -1 and monitoring continued for 24 hours post first dose. All urine produced over the 24 hours before the first dose will be collected for assessment of baseline desmosine levels and for the pre-dose urine PK. [For all timed urine collections, the patients should empty the bladder within 10 minutes of Time 0, discard that urine and then collect all the urine from then onwards. At Time (0 + t hours) they should then empty the bladder and add that to the collection.] On the morning of Day -1, the patients will provide an induced sputum sample; weight of the sample will be recorded, and the sample processed for neutrophils and AZD9668 levels. Blood will also be collected for baseline assessment of hsCRP and serum amyloid A.

Patients will fast from midnight on Day 1 until 2 hours after the first dose (water will be allowed for thirst up until 1 hour before dosing).

On Day 1, pre-dose patients will be asked to provide a spontaneous sputum sample for quantitative bacteriology. They will be randomised to receive either AZD9668 or placebo: A single dose will be administered in the morning of Day 1. All urine produced over the 24 hours after the first dose will be collected for measurement of AZD9668 concentrations. Urine will be collected for time periods 0-4 hours, 4-12 hours and 12-24 hours. Aliquots from each of these collections will be taken for urine PK, and an aliquot from the pooled sample will be taken for urine desmosine. Serial blood samples will be collected for PK analysis at pre-dose and at 0.25, 0.5, 1, 2, 3, 4, 5, 6, 8, 12, and 24 hours post dose (NB. PK samples taken at 24 h will be taken pre-dose). Vital signs and ECG will be done at approximately 1 hour after the first dose.

On Days 2 - 13 the patients will receive 2 daily doses of AZD9668. The first dose of each day will be taken at approximately the same time $(\pm 1h)$ as the first dose administered on Day 1 and the 2nd daily dose will be approximately 12 hours later $(\pm 1 \text{ hour})$.

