Further safety assessments (vital signs, ECG, lung function, haematology, clinical chemistry and urinalysis) will be done before the morning dose on Day 2. Patients will be discharged on the morning of Day 3 (after having taken the 4th dose of the study drug). Prior to discharge,

patients will be re-issued with their BronkoTest[©] diary card and sufficient tablets to allow daily self-dosing until their next visit. Vital signs will be measured and an ECG recorded before discharge. The pharmacogenetic sample can be taken at any convenient time point after the first dose.

The BronkoTest[®] diary card will be filled in for all days whilst the subject is in the CPU and at home.

Visit 3: Treatment period (Day 7 ±1 day): Patients will attend the CPU on the morning of Day 7 (±1 day) in fasted state, having fasted from midnight (water will be allowed for thirst up until 1 hour before dosing) and having withheld taking their morning dose of study medication for that day. Patients will bring with them their BronkoTest[®] diary card and any remaining study medication. Before administration of the morning dose, safety assessments (vital signs, ECG, lung function, haematology, clinical chemistry, urinalysis and urine drug screen) will be performed. Blood samples will be collected pre-dose for PK and for assessment of hsCRP and serum amyloid A. Patients will then take their morning dose of study medication in the CPU. Patients will be discharged from the CPU with their BronkoTest[®] diary card and sufficient tablets to allow daily self-dosing until their next visit.

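### Minor: the 24-hour post-dose cardiac recording is complete on the morning of Day 2 but need only be read before discharge on Day 3, so in-unit doses 3 and 4 can precede the read

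*Protocol*

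**What the plan says.** Section 4.7.3.1 (Telemetry) has the recorder worn "from 24 hours pre-dose to 24 hours post first dose at Visit 2". It sets two review points: the "Investigator or delegate will review and evaluate the recordings before dosing, and before discharge". It adds: "A print-out will be signed and dated by the Investigator and filed with the CRF".

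Section 3.1 (Visit 2) fixes the dosing around this. There is one morning dose on Day 1. On Days 2 to 13 "the patients will receive 2 daily doses of AZD9668". The morning dose is taken within ±1 h of the Day 1 clock time, and "the 2nd daily dose will be approximately 12 hours later", also ±1 h. On leaving the unit it says: "Patients will be discharged on the morning of Day 3 (after having taken the 4th dose of the study drug"). Section 3.4.2 and Table 1 footnote a confirm that dose 4 is taken in the unit and that patients are resident from Day -1 to the morning of Day 3.

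The other cardiac checks at Visit 2 are vital signs and an ECG about 1 h after dose 1, safety assessments including an ECG that "will be done before the morning dose on Day 2", and on Day 3: "Vital signs will be measured and an ECG recorded before discharge".

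Neither the Visit 2 text nor Table 1 gives an earlier review time for the recording. Amendment 01, as shown, does not change the review sentence.

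**The concern.** The recording finishes about a day before the latest time at which it must be read, and two doses fall in between. When a safety recording is read relative to dosing is protocol content and would not normally be left to the SAP.

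It deserves a line because findings of this kind have stopped dosing in this programme. In the multiple-dose volunteer study (section 1.1), 2 of the 18 subjects on active drug (three groups of 6) were withdrawn for rhythm findings: one for symptomless nocturnal bradycardia on 30 mg, one for a run of premature atrial contractions on 70 mg. Section 3.2.2 lists such abnormalities among those noted on 24-hour ambulatory monitoring. In the single-dose part, one subject on 120 mg had a 2-second run of broad-complex tachycardia. Events that are silent or last seconds can be missed by a brief resting 12-lead ECG, and the pre-dose recording cannot show an on-drug event. A silent finding in the post-dose recording could be acted on two doses sooner than the text requires.

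**Working it through.** No sample size, power or error rate is involved; the check is a timeline. Hours are counted from dose 1.

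**Inputs.** Recording window and review points: section 4.7.3.1. Dose times, windows and discharge: section 3.1. Half-lives: section 3.2.1.

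| Event | Nominal (h) | Range with ±1 h windows (h) |
|---|---|---|
| Recording ends | 24 | – |
| Dose 2 (Day 2 morning) | 24 | 23–25 |
| Dose 3 (Day 2 evening) | 24 + 12 = 36 | 23 + 11 = 34 to 25 + 13 = 38 |
| Dose 4 (Day 3 morning) | 48 | 47–49 |
| Discharge, latest required read | after dose 4 | – |

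**Time from end of recording.**
- To dose 3: 36 − 24 = 12 h (34 − 24 = 10 to 38 − 24 = 14 h).
- To dose 4: 48 − 24 = 24 h (23 to 25 h).

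**Dose affected.** Doses 3 and 4: 2 × 60 mg = 120 mg. Dose 2 can also precede the read, but it falls due as the recording ends. It could follow the read only if it were delayed or an interim read were made, so it is not counted.

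**Share of planned dosing.**
- Planned doses: 1 (Day 1) + 2 × 12 (Days 2–13) + 1 (Day 14) = 26.
- After the present latest read: 26 − 4 = 22.
- After a read before dose 3: 26 − 2 = 24.

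**Effect on PK of omitting dose 3 after a late read.**
- The Day 1 profile is untouched, because its 24 h sample is drawn before dose 2.
- The next sample is the Day 7 (±1 day) pre-dose trough, nominally at 144 h. The earliest is Day 6 with the −1 h window: 120 − 1 = 119 h.
- Latest in-window time for dose 3: 38 h. Smallest gap: 119 − 38 = 81 h.
- At the longest mean half-life reported, 14.99 h (single dose): 81 / 14.99 = 5.4 half-lives, leaving 2^(−5.4) ≈ 2.4%.
- At the longest mean steady-state half-life, 10.24 h: 81 / 10.24 = 7.9 half-lives.

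**Effect on spacing of giving dose 3 late instead.** A 6 h delay puts dose 3 at 36 + 6 = 42 h, so dose 4 follows after 48 − 42 = 6 h. A longer delay brings 120 mg closer together still.

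**The case against.** The strongest reply is that nothing here is misstated. The text sets latest review points and does not stop a site reading the recording on Day 2. The present review point sits before the patient goes home to self-dose, which is the decision that matters most. Doses 3 and 4 are taken under supervision. Volunteers received single doses up to 150 mg and 120 mg once daily for 8 days. The 24 h pre-dose recording is read before dose 1. Amendment 01 lowered the permitted ectopics from 15 to 6 per minute, excluded coronary disease and cardiac failure, and added QTcF discontinuation and stopping rules. The discontinuation criteria contain no rhythm threshold that a telemetry finding would trigger. Section 3.2.2 sees no reason to suspect that the volunteer rhythm events were drug-related and notes similar baseline abnormalities in those subjects.

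Most of this stands, and it is why the point is minor. It does not remove the point. A permitted early read is not a required one. Prior exposure was in healthy subjects, not COPD patients. Discontinuation on investigator or sponsor safety judgement is available, so the recording can change dosing without a numeric threshold.

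A reader might infer three stronger things that the documents do not support: that patients go home on an unread recording (the read must precede discharge), that the protocol delays or forbids reading (it does neither), or that the drug is known to cause arrhythmia (section 3.2.2 says otherwise).

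The words on review before dosing could also be taken to mean every dose, which would close the gap. The natural reading is the first dose; if more was meant, the sentence still needs rewording.

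**Conclusion.** The point holds as a small, cheap improvement to when a safety recording is read. A site following sections 4.7.3.1 and 3.1 to the letter may give two in-unit doses (120 mg in total), about 12 h and 24 h after the post-dose recording has ended, before anyone has to read it. Reading it before dose 3 moves 2 of 26 doses to the safe side of the review.

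This rests on three assumptions: that review before dosing refers to the first dose; that doses are given near their scheduled times; and, for the PK cost, that half-lives in COPD patients are not much longer than the volunteer means. No event rate is estimated, because the documents give none for silent rhythm findings in COPD patients. The point does not extend to dose 2, and it does not show that the schedule is unsafe.

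**What to change.** In section 4.7.3.1 replace the review sentence with: *The Investigator or delegate will review and evaluate the pre-dose recording before the first dose, and the 0–24 h post-dose recording on Day 2 before the evening dose (dose 3).* Keep the signed print-out, due by discharge. Add the same review point to the Visit 2 text in section 3.1. Dose 2 stays as scheduled.

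Add a rule for a late read: *If the review is not complete by the end of the dose 3 window, dose 3 is omitted and recorded, and dosing resumes with dose 4 at its scheduled time once the review is done.* Omitting is better than giving dose 3 late. An open-ended delay would set no limit on how close doses 3 and 4 could come, and the estimated margin to the daily exposure limit is only 1.4 (section 3.2.1). Under this rule the nominal 12 h spacing stays, and no gap is shorter than the existing windows already allow (47 − 38 = 9 h at the extreme).

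The cost is two short text changes, with the same recorder, reviewer and print-out; a same-day read within about 12 h (10–14 h) while the patient is resident; and, rarely, one of 26 doses omitted. An omitted dose leaves the Day 1 PK profile untouched and has a negligible effect on the Day 7 trough.
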